NOTE: Risks or harms can be physical, psychological, financial, social, or legal. They may involve breaches of confidentiality and privacy. Do not include the risks of usual care unless usual care is part of the research interventions being performed.

3. What are the anticipated benefits, if any, to participants or to society from this project?

(List in bullet or number format)

1. Potential improvement in CG well-being, stress management, and work functioning
2. Potential improvement in the quality of the Veterans' care.

4. Briefly describe the procedures for the orderly withdrawal or termination of subjects if this study involves any medical therapy. N/A

5. Will any of the following be administered to participants or will they be exposed?

	YES	NO
Ionizing Radiation		
Radioactive Materials		

6. Check one of the boxes below based on your study design and provide the references from the protocol for the information in the table:

Prospective Study Retrospective Study Both

NOTE: If retrospective is checked, some of the below categories may not apply and can be marked as "Not applicable."

Safety Issues	Reference the protocol page and section.	If not referenced in the protocol, cite document type, page and section where it is referenced.
What Safety Information is Collected	p. 8, Section 4, #7	
How will Safety Information be collected	p. 8, Section 4, #7	
Frequency of Safety Data Collection	p. 8, Section 4, #7	
Safety Conditions that Trigger Immediate Suspension of Research	N/A	
Procedures to notify participants or PCP of findings affecting participants' health or welfare	N/A	
Procedures to minimize risk	p. 4, Section 4, #1-4; p. 31, Section 16, #4.1.2	
Inclusion Criteria	p. 34, Section 7, #7	
Exclusion Criteria	p. 34, Section 7, #7	

7. Will an independent Data Safety Monitoring Board (DSMB) or a Data Monitoring Committee (DMC) monitor the project? Yes No

7.1. If yes, provide a description of responsibilities to include frequency of meetings:
As part of HSR&D's Just in Time process, we have been instructed to submit a Data Analysis Plan (DAP) in order to determine assignment to a DSMB (see Appendix 4 for DAP). Once we receive feedback and guidance from HSR&D, we will submit a protocol modification with greater detail regarding frequency of meetings, etc.

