B.1 Screening, Baseline and 4 and 9 month Follow-up Research Assessment Procedures: Once the CG is identified (by self-referral, VA providers, or VINCI), indicates an interest in study participation, and consents (in-person or by phone), the RA will complete the initial screening and, if the CG is eligible, the baseline research assessment. Next, to ensure blinding of the RAs, the Project Coordinator will use a random number table to inform each CG of their group assignment. Procedures for the assigned study arm will commence (see B.2 and B.3). All CGs will be contacted again for 4- and 9-month follow-ups, at which point the majority of baseline assessments will be re-administered. Before each assessment, RAs will remind CGs not to disclose their assigned study arm. Data on care recipients' (CRs') health and service utilization will be extracted from the CRs' clinical record via VINCI, while CG VA and non-VA CG/CR health

and service utilization will be captured by CG assessment. All research assessments (including follow-ups) will be completed by the RA by telephone (with an email/mail-in option, if preferred) and include validated questionnaires regarding CR- and CG-level sociodemographic, clinical, work- related, and psychosocial variables (Appendix 1; Table 1). In-depth qualitative interviews will be conducted at 4-month follow-up with a subgroup of CGs (n=30) from the SOS arm.

These qualitative interviews will be audio recorded.

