B.2 Caregiver SOS Intervention Procedures: SOS care is a comprehensive approach to helping CGs gain the knowledge, skills and confidence to achieve success in stress self- management. The intervention concept was developed by [name] and her research group and will be adapted for the VA context. Through a range of techniques, CGs develop abilities to modify psychological and social sources of stress, including the stress associated with performing both caregiving and work roles. SOS care is brief, telephonic care (6 one-hour sessions over 3-4 months) offered during either work or non-work hours, and tailored to the CG's needs, preferences, and priorities. Supportive visual aids and CG workbook material are distributed via mail or email. SOS is delivered by SOS-trained VA CMs; clinicians with a Master's degree or higher in Social Work or Psychology. SOS care is an opportunity for CGs to form an alliance with a VA healthcare professional ready to meet their health and psychosocial needs, including concerns about CR health and treatment.

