B.3. UC Comparator Procedures: CGs in this arm will be contacted telephonically once by a CM. After a brief needs assessment, the CM will provide contact information for appropriate VA (e.g., local CSP clinicians) and non-VA community resources/services. CGs will be sent brochures for the national VA CSP. Information on both the program's website (which includes links to training, education, resources, and outreach programs for CGs) and the national CG hotline number will be included in the e/mailed packet. Receipt of information regarding the VA CSP is consistent with the standard of care for informal CGs in the VHA since 2010.³⁰ After this initial contact, CGs in this group will only be contacted again 4 and 9 months after baseline for administration of follow-up research assessments. CGs will be encouraged to seek medical, psychological, social support, and social services that are available to them through VAMCs or any other non-VA/community source. CGs in the SOS group will be offered similar information.

B.4. Training and Supervision: The SOS care CM will have 16 hours of training (telephone and webinar) that will cover the study protocols, modules, assessment tools, care documentation and performance standards. Training will continue during team supervision sessions (telephone

and webinar) and on an individual ad hoc basis (with Drs. [name], [name], and [name]).

Supervision sessions, held weekly, will involve review of specific cases.

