All protocol deviations, breaches of confidentiality, adverse events or other problems will be identified and reported to the local site's IRB, Privacy Officer, and/or Information Security Officer after discovery, as stipulated by regulations. All breaches of confidentiality will be immediately (within 1 hour) reported to the ISO and Privacy Officer. Non-serious adverse events and anticipated adverse events and problems will be logged and discussed in the routine supervision of research staff. The PI will initiate review of concerns arising from the ongoing review of non-serious and anticipated adverse events that appear to impact the study/risk ratio on an ad hoc basis. All serious adverse events and non-serious unexpected events will be reported to the PI and IRB in accordance with Good Clinical Practice Guidelines and IRB Regulations. Severe adverse events (SAEs) (e.g., hospitalization, death), will be reported to the PI within 24 hours and to the IRB within 48 hours. Unexpected adverse events will be reported to the IRB within 72 hours. Minor and anticipated adverse events and problems will be logged and reported in the annual/continuing review to the IRB.

The Principal Investigator will be responsible for reviewing any adverse events or issues with the protection of subjects. Should there be a need for a clinical intervention, one of the clinicians on the study ([name], [name], [name], or [name]) will provide said intervention.

12. Privacy and Confidentiality

12.1. Describe whether the study will use or disclose subjects' Protected Health Information (PHI).

Veteran/CG PHI and identifiers (e.g., first, middle, last names; SSN's; addresses and phone numbers; date of birth; age over 90 years; ID numbers/medical record numbers; and dates/procedural codes associated with health service utilization and pharmacy records) extracted from CPRS or VINCI will remain in the designated study folder on the MIRECC or VINCI secure servers. PHI will primarily be used for recruitment and tracking purposes. PHI will not be disclosed.

12.2. Describe the steps that will be taken to secure the data (e.g., training, authorization of access, password protection, encryption, physical controls, Certificates of Confidentiality, and separation of identifiers and data)

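### No adverse-event questioning applied alike in both arms is described, and SOS has 8 scheduled contacts against 3 in usual care, so logged events by arm are open to ascertainment bias

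*Combined protocol and SAP*

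**What the plan says.** **How events are recorded.** Section 16, item 11.1 states that "adverse events or other problems will be identified and reported to the local site's IRB, Privacy Officer, and/or Information Security Officer after discovery". For the milder ones, "Non-serious adverse events and anticipated adverse events and problems will be logged and discussed in the routine supervision of research staff". The principal investigator starts an ad hoc review when the accumulating events raise a concern about risk. Serious events go to the investigator within 24 hours and to the IRB within 48. The item does not say who asks caregivers about events, with what question, or when.

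**Where collection should be described.** The Section 4, item 6 table has rows for what safety information is collected, how it is collected, and "Frequency of Safety Data Collection". All three point to Section 4, item 7. That item asks about a monitoring board; its answer says that board assignment is pending and that detail will follow in a protocol modification.

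**Contacts by arm (Section 16, item 4.3.1).**
- B.2, intervention: "SOS care is brief, telephonic care (6 one-hour sessions over 3-4 months").
- B.3, usual care: "CGs in this arm will be contacted telephonically once by a CM". On content: "After a brief needs assessment, the CM will provide contact information for appropriate VA" and other resources. After that, "CGs in this group will only be contacted again 4 and 9 months after baseline".
- B.1, both arms: "All CGs will be contacted again for 4- and 9-month follow-ups". Research assistants who are meant to be blind to arm carry these out, with mail, email or (item 8.1) Qualtrics completion as alternatives.

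**The concern.** If events are recorded when a caregiver happens to mention them, the number recorded depends on how often, and how fully, caregivers talk to study staff. SOS caregivers spend six hours in one-to-one conversation about stress, work and the care recipient. Their care manager documents each contact, and cases are reviewed in weekly supervision. A usual-care caregiver has one call and then nothing scheduled until month 4. One of the two risks listed in Section 4 is discomfort from questions about psychological concerns or caregiving, so the named harm is also the one most visible in the arm where those topics are discussed.

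At stake is the reading of the safety record. With equal true risk, SOS may appear to have more events. Conversely, a real excess in SOS could be dismissed as a product of closer contact. The investigator's continuing risk review, any monitoring board, and a final table of events by arm would all draw on the same unequally gathered log.

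**Working it through.** The plan states no adverse-event rate, capture rate or safety test, so there is no figure to reproduce. The check has three parts: a contact count, a search for another route into the log, and an illustration of how far contact frequency could matter.

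**1. Scheduled contacts after randomization (Section 16, item 4.3.1, B.1 to B.3)**

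| | SOS | Usual care | Ratio |
|---|---|---|---|
| Care-manager calls | 6 | 1 | 6.0 |
| Through the 4-month assessment | 6 + 1 = 7 | 1 + 1 = 2 | 3.5 |
| All, including 4 and 9 months | 6 + 2 = 8 | 1 + 2 = 3 | 2.7 |

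SOS care time is 6 × 60 = 360 minutes. The length of the usual-care call is not stated.

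**2. Other routes into the log**

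Item 11.1 names no route. Staff contact is therefore an inference, but the supplied text describes no alternative. Item 4.3.2 fits it: the team has guidelines for distress that emerges on the telephone. Caregiver-reported service use is collected at 4 and 9 months in both arms, but nothing links it to event review.

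**3. Illustration, on assumed values only**

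Assume equal true risk in both arms, event times uniform over 0 to 9 months, SOS calls evenly spaced to month 4, and the usual-care call at 0.25 months. Each contact after an event brings it to light independently with probability q, and the 4- and 9-month assessments work as well as a care call. An event with k contacts still to come is then logged with probability 1 − (1 − q)^k.

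- SOS: k = 8, 7, 6, 5, 4, 3 in six successive intervals of 4/6 = 0.667 months, then k = 1 from month 4 to 9.
- Usual care: k = 3 for 0.25 months, k = 2 for 3.75 months, then k = 1 for 5 months.

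For q = 0.1:
- Usual care: (0.25 × 0.271 + 3.75 × 0.190 + 5 × 0.100) / 9 = 0.142.
- SOS: (0.667 × (0.570 + 0.522 + 0.469 + 0.410 + 0.344 + 0.271) + 5 × 0.100) / 9 = 0.247.
- Ratio: 0.247 / 0.142 = 1.74.

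| q | Logged share, SOS | Logged share, usual care | Ratio, months 0–9 | Ratio, months 0–4 |
|---|---|---|---|---|
| 0.1 | 0.247 | 0.142 | 1.74 | 2.21 |
| 0.2 | 0.416 | 0.275 | 1.51 | 1.86 |
| 0.3 | 0.536 | 0.397 | 1.35 | 1.60 |
| 0.5 | 0.704 | 0.615 | 1.15 | 1.27 |

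The result turns on what the shared assessments pick up. If they bring no events to light, almost every logged event comes from SOS (ratios of about 27 to 48 for these q). If they bring every event to light, the ratio is 1.00. The direction is consistent; the size follows from the assumptions.

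**The case against.** Four points on the other side carry weight.

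**No planned analysis is affected.** Items 9.1 and 9.2 contain no comparison of adverse events by arm, and item 11.1 concerns reporting and review of concerns without mentioning arms. A reader might infer that a stated safety analysis is biased. The documents do not support that; the risk is to the investigator's review and to later reporting.

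**Both arms share the 4- and 9-month assessments.** A reader might take 6 to 1 as the contrast in contact. Over all scheduled contacts it is 8 to 3. Completion by mail, email or Qualtrics can remove conversation from those assessments, which limits their value for events that are only mentioned in passing, but they remain common to both arms.

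**Caregiver events may be recoverable elsewhere.** A reader might infer that they are not, because record extraction centres on the Veteran. B.1 says caregiver health and service use is captured by caregiver assessment, and item 8.1 says caregiver-related use comes from VINCI or self-report. Item 9.2 describes the survey more narrowly, as asking about the Veteran's non-VA care and the caregiver's support services. Coverage of caregiver hospitalization is unclear, not ruled out.

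**Relevant text is not in hand.** Appendix 1 (instruments) and Appendix 4 (the data analysis plan for board assignment) are cited but not supplied, and item 7 defers monitoring detail. Event questions may exist there.

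These objections narrow the point without removing it. The two places that should describe event collection, item 11.1 and the Section 4 table, do not, and contact is unequal on any count.

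**Conclusion.** The point holds as a weakness in how safety information is gathered. As written, the plan yields an event log built from 8 scheduled contacts per SOS caregiver and 3 per usual-care caregiver, with no described questioning common to both arms. A comparison of logged events by arm would be open to ascertainment bias, probably towards more events in SOS.

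The size cannot be stated. The ratios of 1.15 to 1.74 over 9 months rest on assumed detection probabilities, and other assumptions about the shared assessments move the answer from 1.00 to above 25. A definite inflation factor, or a statement that SOS is bound to show more events, would go beyond the documents.

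Nor should the point be extended to efficacy. K10, C-WLQ and self-reported service use are collected alike at 4 and 9 months, so a comparison of them does not depend on how many care calls bring events to light. The conclusion assumes that the unseen appendices hold no structured event items; if they do, the defect reduces to a missing cross-reference.

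**What to change.** First check Appendices 1 and 4. If they already contain event questions asked alike in both arms, cite them in item 11.1 and in the Section 4 table. If not:

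1. Add a short fixed set of caregiver event questions to the 4- and 9-month assessments, for example hospitalization, emergency visit, and worsening that needed care since the last assessment. Use the same wording in both arms and in every completion mode.
2. Make these answers the primary source for any summary of adverse events by arm. They should not be the only source, because caregivers who die or are lost give no answers. The plan allows up to 20% attrition (150 to 120 per arm, so 30 per arm), and death is a named serious event. Show deaths and numbers lost by arm beside the summary.
3. List events that arise in care-manager calls separately as spontaneous reports, still handled under item 11.1.
4. Point the three rows of the Section 4 safety table to this text.

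With full recall at both assessments the expected ratio under equal risk is 1.00. With incomplete recall, restricting the by-arm comparison to the elicited answers still removes the dependence on care-call frequency.

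The cost is protocol wording and one or two minutes on assessments that already take place, with no added visit or staff. Recall spans 4 months at the first assessment and 9 − 4 = 5 at the second. The change does not bring forward the discovery of serious events in usual care between contacts: one in month 1 may still surface only at month 4.

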
SECTION 17: KEYWORDS

(NOTE: Provide three (3) keywords. Use MeSH Headings only (Central Office Requirement). Enter one item per line. <http://www.nlm.nih.gov/mesh/MBrowser.html>)

1.
2.
3.

SECTION 18: INSTITUTIONAL SUPPORT

(NOTE: If yes is marked next to any Service/Section listed below, you **MUST** obtain the signature of the Service Chief or Designee of any Service/Section involved in research. **OR**, a letter/e-mail should be provided to the investigator from the Service Chief or Designee of any Service/Section involved in this research.)

Laboratory	Yes  No 	Signature OR Letter/E-mail
Pharmacy	Yes  No 	Signature OR Letter/E-mail
Nuclear Medicine	Yes  No 	Signature OR Letter/E-mail
Psychiatry	Yes  No 	Signature OR Letter/E-mail
Medicine	Yes  No 	Signature OR Letter/E-mail
Radiology	Yes  No 	Signature OR Letter/E-mail
Nursing	Yes  No 	Signature OR Letter/E-mail
Outpatient	Yes  No 	Signature OR Letter/E-mail
Union	Yes  No 	Signature OR Letter/E-mail
Lab Space	Yes  No 	Signature OR Letter/E-mail
Other, specify 	Yes  No 	Signature OR Letter/E-mail

SECTION 19: DATA MANAGEMENT AND ACCESS PLAN (DMAP)

NOTE: This Data Management and Access Plan (DMAP) should be used for Unfunded VA Research or VA Research Funded by Entities Without a Specific DMAP.

IF THE FUNDING AGENCY HAS A DMAP, SUBMIT IT, INSTEAD OF THE BELOW.**Section 1 - Funding – (Check applicable box and indicate funding source if present.)**

 VHA Program Office without Specified DMAP Format	Name of Program Office:
 External Funder without Specified DMAP Format	Name of Funder:
 Unfunded	
 Not applicable ; see separate DMAP from funding source	

Section 2 - Public Access to Publications Resulting from the Research - (Check all applicable boxes.)

 The proposed research is to be funded by VA . Publications resulting from the research will be made available to the public through the National Library of Medicine (NLM) PubMed Central website within one year after the date of publication. [Submission procedures are provided on the Office of Research and Development (ORD) website at http://www.research.va.gov/resources/policies/public_access.cfm .]
 1
 The proposed research will not be funded by VA . Publications will be made available to the public through PubMed Central within one year after the date of publication. [See ORD website noted above.]
 Publications will be made available to the public in another way. [Briefly describe plans below.]
Publications will not be made available to the public. [Provide a brief rationale below.]

Additional details related to plans for public access to publications results from the research, as indicated in section 2 above.

Section 3 - Public Access to Final Data Sets Underlying Publications Resulting from the Research - (Check all applicable boxes.)

Final data sets underlying publications resulting from the proposed research will be shared outside VA in electronic format through the mechanism(s) indicated in Items #6 through #10 below.
 VA ONLY in hard copy through the mechanism(s) indicated in Items #6 through #10 below. [Provide a brief rationale below.]
Final data sets underlying publications resulting from the proposed research will not be shared outside VA, except as required under the Freedom of Information Act (FOIA) [Provide the rationale below.]

Additional rationale(s) for plans to access data sets underlying publications, as indicated in Section 3 above.

Section 4 - Mechanisms for Public Access to Final Data Sets Underlying Publications Resulting from the Research – (Check all applicable boxes.)

 As indicated in Item #5 above, final data sets underlying publications resulting from the proposed research will not be shared outside VA.
The project involves basic science research . Final data sets underlying publications resulting from such research will be shared as described in the space below. [Describe mechanisms for sharing, e.g., upon request, through a databank or repository, via a website]

The research involves human subjects . Data sets based on information obtained from human subjects will be shared as	Individually Identifiable Data will be shared pursuant to valid HIPAA Authorization, Informed Consent, and an appropriate written agreement limiting use of the data to the conditions described in the authorization and consent.
---	---

follows. Check appropriate box.

A Limited Dataset (LDS) will be created and shared pursuant to a Data Use Agreement (DUA) that indicates adherence to any applicable Informed Consent provisions, appropriately limits use of the dataset and prohibits the recipient from identifying or re-identifying (or taking steps to identify or re-identify) any individual whose data are included in the dataset. *NOTE: An LDS does not necessarily imply de-identified data per HIPAA.*

	 A De-identified, Anonymized Dataset will be created and shared. NOTE: ORO recommends that such sharing take place under a written agreement that adheres to any applicable Informed Consent provisions and prohibits the recipient from identifying or re-identifying (or taking steps to identify or re-identify) any individual whose data are included in the dataset. However, it is permissible for final datasets in machine-readable format to be submitted to and accessed from PubMed Central (and similar sites) provided that care is taken to ensure that the individuals cannot be re-identified using other publicly available information.
It is likely that requests for data from outside researchers (or other entities) may correspond to one or both of the following special conditions :	 Individually Identifiable Data , excluding Veterans' names and 38 USC §7332-protected information, will be shared, pursuant to a written request and IRB approved waiver of HIPAA authorization, with the approval of the Under Secretary for Health , in accordance with VHA Handbook 1605.1 §13.b(1)(b) or §13.b(1)(c) or superseding versions of that Handbook. Note: Subject to all other listed requirements, Veterans' names may be shared with other Federal agencies (38 USC §5701), and with non-Federal investigators who provide the names and addresses of the individual subjects.  Individually Identifiable Data , including 38 USC 7332-protected information, will be shared, pursuant to the above requirements and a written assurance from the recipient that the information will be maintained in accordance with the security requirements of 38 CFR Part 1.466, or more stringent requirements, the information will not be re-disclosed except back to VA, and the information will not identify any individual patient in any report of the research or otherwise disclose patient identities.

Additional details on mechanisms for sharing final data sets as indicated in Section 4 above.

Section 5 - Briefly summarize how, where, when, to whom, and the extent to which data resulting from the research will be made available outside VA.

Section 5 answer:

Section 6 - Describe how and where data resulting from the research will be stored and maintained (e.g., data will be stored and maintained in a secure ORD data repository or resource; data will be stored on VA servers behind the VA firewall and backed up to a hard drive maintained and secured in the investigator's lab; etc.).

Section 6 answer:

Section 7 - Describe the mechanisms for ensuring the protection of personal privacy, the confidentiality of individually identifiable information, and the security of proprietary data and information.

Section 7 answer:

Section 8 - Describe the scientific and/or public purposes for making the data available (i.e., how will scientists and/or the public benefit from making the data available) **and** explain how the data available for sharing will permit **validation of results** by the recipients (e.g., sufficient data and descriptors will be made available to confirm conclusions in the publication, duplicate statistical analysis, perform additional analyses, etc.).

Section 8 answer:

Section 9 - Describe the mechanisms for ensuring the protection of personal privacy, the confidentiality of individually identifiable information, and the security of proprietary data and information.

Section 9 answer:

Section 10 - Describe the scientific and/or public purposes for making the data available (i.e., how will scientists and/or the public benefit from making the data available) **and** explain how the data available for sharing will permit **validation of results** by the recipients (e.g., sufficient data and descriptors will be made available to confirm conclusions in the publication, duplicate statistical analysis, perform additional analyses, etc.).

Section 10 answer:

Section 11 - As Principal Investigator for the proposed research, I **attest** to the accuracy of the information provided above, and I understand that –

- Final data sets must be maintained locally in accordance with VA Records Control Schedule 10-1 or until enterprise-level resources become available for long-term storage and access (unless otherwise required or permitted by the relevant VHA Program Office)
- Failure to implement this DMAP may result in restrictions to subsequent research activities

SECTION 21: ATTESTATION TO FOLLOW FEDERAL REGULATIONS

As the Principal Investigator for this project, I certify that I have read, understand, and accept the investigator responsibilities as outlined in VHA Handbook 1200.05, paragraph 5g and that these include but are not limited to the following:

- Giving first priority to the protection of human subjects; upholding professional and ethical standards and practices; and adhering to all applicable VA and other Federal requirements, include IRB and the local VA Facility's policies and procedures regarding the conduct of research and the protection of human subjects.
